5. TREATMENT PLAN

Treatment will be administered on an outpatient basis. Expected toxicities and potential risks as well as dose modifications are described in Section 6 (Expected Toxicities and Dosing Delays/Dose Modification).

The treatment plan is outlined in the table below. Tivozanib will be taken orally once daily for 3 out of 4 weeks on a continuous basis. Enzalutamide will be taken orally once daily without any scheduled interruptions, on a continuous basis.

| Treatment Description | | | | | | |
|-----------------------|-------------|--------|---------------|------------|-----------------|--|
| Agent | Precautions | Dose | Route | Schedule | Cycle Length | |
| Tivozanib | None | 1.5 mg | PO once daily | Weeks 1-3 | | |
| Enzalutamide | None | 160 mg | PO once daily | Continuous | 28 days | |

Because this combination has not been previously tested, a safety run-in will be conducted at the outset of the trial. After the first 3 patients are enrolled, accrual will be held until all three patients complete the first 1 month of treatment. Additionally, after a total of 10 patients are enrolled, these patients will be analyzed for safety and toxicity by the DSMC. If any treatment-related, expected or unexpected grade 3 or higher adverse events occur during the first month of treatment in the first 3 patients, or if the rate is >30% among the first 10 patients during the first month of treatment, further accrual will be halted for reconsideration of the appropriateness of the dosing schedules.

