5.1.2 Day 1 of Every 3rd Cycle

The following data should be collected on Day 1 (+/- 3 days) of every 3rd cycle (see Schedule of Events):

- History and physical examination
- ECOG performance status
- Vital signs (including blood pressure, body temperature, heart rate and respiratory rate)
- Complete blood count
- Serum chemistries
- Thyroid function test (TSH only; every odd number Cycle beyond Cycle 1 up to Cycle 46 and then every 3rd Cycle)
- Urinalysis (urine protein only)
- Serum PSA
- Concomitant medications
- Adverse event assessments
- Study drug diary

[Note: If ECOG performance status, physical examination, hematology, serum chemistry, coagulation studies, and urinalysis were measured/performed within 7 days prior to Cycle 1, Day 1, they need not be repeated at that visit.]

If any treatment-related grade ≥ 3 non-hematologic or grade ≥ 4 hematologic adverse events are observed, then treatment should be held until resolution of the event(s) to \leq grade 2. The attribution of the events to either or both of the study drugs will be at the discretion of the treating physician, and only the responsible drug should be held. Doses that are held will not be

made up, and the cycle number and cycle day will continue chronologically regardless of whether treatment is held.

If either study drug is held for \geq 4 weeks, regardless of cause, then the patient should be removed from study treatment.

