5.2.2. Enzalutamide

Patients will be treated with 160 mg/day of enzalutamide, taken orally.

Enzalutamide has the chemical name 3-(4-cyano-3-trifluoromethylphenyl)-1-[3-fluoro-4 (methylcarbamoyl)phenyl]-5,5-dimethyl-2-thioxoimidazolin-4-one. The drug substance has no chiral centers and no salt forms are available at ~ pH 2 to 10. It is essentially insoluble in water, but partially soluble in lipid-based solutions.

Study drug doses should be taken at approximately the same time each day. If dosing is missed on one day for any reason, including vomiting of the dose, the dose should not be repeated or made up. On days of a scheduled clinic visit, the dose of enzalutamide should not be taken until after visit procedures are completed. Dosing will be on a continuous basis unless drug-related adverse events are noted as described in Section 5.1.

Study drug should be stored in a secure location with limited access within the following temperature range: 59°F to 86°F (15°C to 30°C). Bottles should be labeled with the study protocol number, medication or kit number, contents, directions for use, expiration date, and storage directions. Patients will be instructed to store study drug at room temperature out of the reach of children. The drug substance is formulated in the surfactant Labrasol to create a self-emulsifying (or microemulsifying) dosage form. The product will be provided as gelatin capsules in bottles with child-resistant caps.

Patients will be asked to keep a drug diary to document their daily dosing. Study drug accountability will be performed at study visits every 12 weeks to document compliance. Any remaining capsules should be returned at the study visit that will occur every 12 weeks.

Enzalutamide can be taken without regard to other food or beverage intake, and may be taken before or after tivozanib.

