6.2 Tivozanib Dose Modification

Clinical judgment will be used to determine appropriate management of the subject experiencing any adverse event (AE). The suggested criteria for dose modification for tivozanib hydrochloride drug-related AEs (excluding hypertension) are summarized in the table below.

Tivozanib Hydrochloride Dose Modification Guidelines for Drug-Related Adverse Events

| Drug-Related Adverse | Action Taken | Subsequent Dosing Modification |
|-----------------------------|--|---|
| Events (excluding | | |
| Hypertension ^a) | | |
| Grade 1 | No dose interruption, or reduction required; adverse event management is at the discretion of the Investigator | None required; Dosing may continue at the same dose |
| Grade 2 | No dose interruption, or reduction required; adverse event management is at the discretion of the Investigator | None required; Dosing may continue at the same dose |
| Grade 3 | Interrupt dosing until toxicity resolves to baseline. | Dosing may resume at same dose or reduced dose at the discretion of the Investigator (see below for dose reduction guidelines). |
| Grade 4 | Interrupt dosing until toxicity resolves to baseline. | Dosing may resume at same dose or reduced dose at the discretion of the investigator (see below for dose reduction guidelines). |

^a Hypertension must be treated as described in Section 6.2.1 prior to any dose modification

If a patient experiences unacceptable toxicity related to tivozanib at 1 mg/day, he should be removed from study. Once the dose of tivozanib is reduced, it should not be re-escalated throughout the study.

Subjects with clinically significant Grade 3/4 AEs that are assessed as possibly, probably or definitely study drug-related by the Investigator should have their dose interrupted to allow for resolution of toxicities to baseline. The exception is HTN, which must first be treated as described in Section 6.2.1 prior to any dose modification. Tivozanib may be held for up to 4 weeks. If any drug-related toxicity results in interruption of > 4 weeks, the subject should be discontinued from the study.

Dose escalation of tivozanib above 1.5 mg/day will not be allowed.

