6.4 Enzalutamide Dose Modification

Dose modification of enzalutamide will generally not be permitted. Patients who experience Grade 3 or greater toxicity related to enzalutamide that cannot be ameliorated by the use of adequate medical intervention should have treatment interrupted until the toxicity improves to Grade 2 or lower severity. A treatment break of up to 4 weeks is permitted. If a patient experiences unacceptable toxicity related to enzalutamide at 160 mg/day, he should be removed from study unless specific permission to restart at a reduced dose is granted by the PI.

Dose escalation of enzalutamide above 160 mg/day will not be allowed.

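### Sections 5.1.2 and 6.4 set different hold triggers for enzalutamide-related events that respond to treatment, with no rule of precedence; 5.1.2 also omits the hypertension exception

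*Combined protocol and SAP*

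**What the plan says.** **General hold rule.** It stands at the end of Section 5.1.2, a section otherwise given to visit data: "If any treatment-related grade ≥ 3 non-hematologic or grade ≥ 4 hematologic adverse events are observed, then treatment should be held". The hold lasts until grade 2 or lower. The treating physician decides which drug is responsible, and only that drug is stopped. Missed doses are not made up. If either drug is held for four weeks or longer, "regardless of cause, then the patient should be removed from study treatment".

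**Enzalutamide rule.** Section 6.4 says that patients with "Grade 3 or greater toxicity related to enzalutamide that cannot be ameliorated by the use of adequate medical intervention should have treatment interrupted". The point at which the break ends is the same as in 5.1.2, namely "until the toxicity improves to Grade 2 or lower severity".

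**Cross-references.** The introduction to Section 5 says: "Expected toxicities and potential risks as well as dose modifications are described in Section 6". Section 5.2.2 says of enzalutamide: "Dosing will be on a continuous basis unless drug-related adverse events are noted as described in Section 5.1".

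**Hypertension on tivozanib.** Section 6.2 leaves hypertension out of its dose-modification table: "The suggested criteria for dose modification for tivozanib hydrochloride drug-related AEs (excluding hypertension) are summarized in the table below". After the text rule that clinically significant related grade 3 or 4 events should lead to interruption, it adds: "The exception is HTN, which must first be treated as described in Section 6.2.1 prior to any dose modification". Section 6.2.1 asks for antihypertensive drugs before any dose reduction. It also counts as grade 3 any worsening of controlled baseline hypertension that needs more intensive therapy.

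**The concern.** A hold rule should give the same answer wherever a site looks it up. Here two sections cover the same enzalutamide-related event with different conditions. Section 5.1.2 acts once the event is observed. Section 6.4 acts only if medical treatment fails. The two cross-references point in opposite directions.

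Take grade 3 diarrhea that the physician attributes to enzalutamide and that settles with anti-diarrheals. A site that follows the Section 5 introduction to Section 6 may keep dosing. A site that follows 5.2.2 to Section 5.1 holds the drug. The exposure lies with the site that does not hold, in a combination that is being given for the first time.

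For hypertension the direction reverses: a literal reading of 5.1.2 stops tivozanib before the antihypertensive step that 6.2 puts first.

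**Working it through.** No calculation applies. The check is a comparison of the rules, followed by a search for anything that ranks them.

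**Step 1. Triggers side by side.** All events are taken as related to the drug named.

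| Event | 5.1.2 | 6.4 or 6.2 | Same action? |
|---|---|---|---|
| Enzalutamide, grade ≥3 non-hematologic or grade ≥4 hematologic, responds to treatment | Hold | 6.4: interruption not required | No |
| The same event, does not respond | Hold | 6.4: interrupt | Yes |
| Enzalutamide, grade 3 hematologic, responds | No hold directed | 6.4: interruption not required | Yes |
| Enzalutamide, grade 3 hematologic, does not respond | No hold directed | 6.4: interrupt | 6.4 adds a rule that 5.1.2 lacks |
| Tivozanib, grade 3 hypertension | Hold | 6.2: treat first, before any dose modification | No |

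The first row is the main point. The fourth is not part of it, but the fix has to preserve that rule.

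**Step 2. Is the first row a contradiction?** Section 6.4 does not tell anyone to keep dosing. That no hold is needed follows only from its condition. Holding therefore satisfies both sections, while continued dosing satisfies 6.4 alone. Both sections word the instruction as *should*.

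**Step 3. Does the protocol rank the sections?** The Section 5 introduction favours Section 6, 5.2.2 favours Section 5.1, and no other sentence gives precedence. The cross-references leave the question open.

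**Step 4. What differs in practice?** Both sections restart enzalutamide at grade 2 or lower. The difference for one event is the daily doses missed between its observation and its return to grade 2 or lower.

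**Step 5. Does related grade 3 hypertension meet the 5.1.2 trigger?** Yes. It is non-hematologic, and 6.2.1 assigns grade 3 to some men on worsening alone. Section 5.1.2 neither states the treat-first exception nor refers to it. In 6.2 the exception directly follows the interruption rule, so it covers holds as well as dose reductions.

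**Step 6. Does any planned figure depend on this?** No. Section 14.1 defines PFS by progression or death. Its run-in rule counts related grade ≥3 events in the first month whether or not drug was stopped.

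**The case against.** The strongest reply is that a site that reads the whole protocol will hold enzalutamide, because 5.2.2 leads to the hold rule and 6.4 never forbids a hold. That stands, and it limits the point. A reader might infer that the sections are irreconcilable and that no site can comply with both; the documents do not support this. What remains is that a site working from Section 6, as the Section 5 introduction directs, would not meet the stricter rule there.

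On hypertension, the reply is that treat-first appears in the 6.2 table footnote, the 6.2 text and 6.2.1, each time with *must*, against *should* in 5.1.2. The specific rule would probably be followed. The Appendix C flow chart is not visible in the text reviewed and may contain hold steps of its own. This also stands: the finding is an omission in 5.1.2, and the practical effect cannot be established.

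A reader might also turn the background rates into a count of men wrongly held. The documents do not allow it. The hypertension figures, 22.2% in the combination studies (Section 2.1.1.3) and 42.4% in the pooled renal cell monotherapy studies, are not broken down by grade. Section 6.3 gives its enzalutamide rates without grades and reports similar numbers of events on enzalutamide and placebo.

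Finally, 6.4 may have been meant to put medical management first. Only the sponsor can say. That is a reason to state one rule, not to leave two.

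**Conclusion.** The point holds in a limited form. For enzalutamide-related grade ≥3 non-hematologic or grade ≥4 hematologic events that respond to treatment, 5.1.2 directs a hold, 6.4 does not require one, and nothing settles which governs. Section 5.1.2 also lacks the hypertension exception of 6.2, though that gap is less likely to change practice.

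Per event, the size is the enzalutamide doses missed until grade 2 or lower, with removal from treatment under 5.1.2 if the hold reaches four weeks. The number of men affected cannot be estimated.

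A reader might infer a threat to the primary result or to the run-in. The definitions do not support that, and no analysis figure changes. This is an inconsistency in operative safety instructions that should be corrected because the remedy is cheap. The conclusion rests on the wording alone and assumes that the Appendix C figure does not supply the missing rule for 5.1.2.

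**What to change.** Two changes in wording:

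1. **Section 6.4**, give it the trigger of 5.1.2: *Hold enzalutamide for any related grade ≥3 non-hematologic or grade ≥4 hematologic event until grade 2 or lower, with medical treatment given meanwhile. For related grade 3 hematologic toxicity, interrupt only if adequate medical treatment fails to improve it.*
2. **Section 5.1.2**, add: *Exception: tivozanib-related hypertension is first treated as described in Sections 6.2 and 6.2.1 and Appendix C before any hold.*

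The first change makes the answer the same for the disputed events whichever cross-reference a site follows, so 5.2.2 can stay as it is. It takes the stricter rule because the combination is new, and it keeps the existing 6.4 rule for grade 3 hematologic events. The tivozanib triggers in 6.2 should stay as written, since a further trigger there could clash with its table.

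The cost is a short amendment, which Section 13.1 requires the IRB to approve before use, and some brief enzalutamide holds for events that would have settled with dosing continued.

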5.1.3 Off Study Visit

The following data should be collected during the off study visit:

- History and physical exam
- Concomitant medications
- Vital signs (including blood pressure, body temperature, heart rate and respiratory rate)
- ECOG performance status
- Serum PSA
- Complete blood count
- Serum chemistries
- Urinalysis (protein only)
- Bone scan and abdominal/pelvic CT scans (performed if an assessment has not been performed within the prior 6 weeks)
- Adverse event assessments

5.2 Drug Administration and Formulation

5.2.1. Tivozanib

Patients will be treated with 1.5 mg/day of tivozanib, taken orally once daily for 3 weeks, followed by 1 week off tivozanib (1 cycle = 3 weeks on, 1 week off). One cycle is defined as 4 weeks. Cycles will be repeated every 4 weeks in the absence of disease progression or unacceptable toxicities.

Tivozanib should be taken at approximately the same time every day, preferably in the morning, with up to 200 mL of water. Tivozanib should be taken at least 1 hour before or 2 hours after ingesting any food or other medications. On days of a scheduled clinic visit, the dose of tivozanib should not be taken until after visit procedures are completed. If a dose is vomited or missed the dose should not be made up. Only one tivozanib capsule should be taken each day. Grapefruit and grapefruit juice should be avoided during the study.

In the event that tivozanib hydrochloride dosing is interrupted, the duration of cycle/treatment will not be extended; doses missed during the interruption will be captured as omitted rather than delayed.

5.2.2. Enzalutamide

Patients will be treated with 160 mg/day of enzalutamide, taken orally.

Enzalutamide has the chemical name 3-(4-cyano-3-trifluoromethylphenyl)-1-[3-fluoro-4 (methylcarbamoyl)phenyl]-5,5-dimethyl-2-thioxoimidazolin-4-one. The drug substance has no chiral centers and no salt forms are available at ~ pH 2 to 10. It is essentially insoluble in water, but partially soluble in lipid-based solutions.

Study drug doses should be taken at approximately the same time each day. If dosing is missed on one day for any reason, including vomiting of the dose, the dose should not be repeated or made up. On days of a scheduled clinic visit, the dose of enzalutamide should not be taken until after visit procedures are completed. Dosing will be on a continuous basis unless drug-related adverse events are noted as described in Section 5.1.

Study drug should be stored in a secure location with limited access within the following temperature range: 59°F to 86°F (15°C to 30°C). Bottles should be labeled with the study protocol number, medication or kit number, contents, directions for use, expiration date, and storage directions. Patients will be instructed to store study drug at room temperature out of the reach of children. The drug substance is formulated in the surfactant Labrasol to create a self-emulsifying (or microemulsifying) dosage form. The product will be provided as gelatin capsules in bottles with child-resistant caps.

Patients will be asked to keep a drug diary to document their daily dosing. Study drug accountability will be performed at study visits every 12 weeks to document compliance. Any remaining capsules should be returned at the study visit that will occur every 12 weeks.

Enzalutamide can be taken without regard to other food or beverage intake, and may be taken before or after tivozanib.

5.3 General Concomitant Medication and Supportive Care Guidelines

The only permitted concurrent anticancer therapy during study treatment is ongoing GnRH agonist therapy (e.g. leuprolide, goserelin, etc.). Subjects should avoid agents known to be Cytochrome P450 (CYP3A4) inducers or inhibitors for the duration of study treatment. See Appendix B for a list of CYP3A4 inducers and inhibitors.

5.3.1. Hormonal agents

Ongoing GnRH agonist therapy is required, unless a patient has undergone surgical castration. Prior treatment with other hormonal agents, such as antiandrogens, ketoconazole, orteronel or abiraterone, must have been stopped a minimum of two weeks prior to study entry. No prior therapy with enzalutamide, TOK-001, or ARN-509 is permitted.

5.3.2. Other anticancer therapy

Concurrent treatment with chemotherapy, immunotherapy or other cancer-directed treatment is not permitted. Prior chemotherapy for metastatic CPRC must have finished at least three weeks prior to initiation of treatment on this study. Prior treatment with sipuleucel-T is permitted, and must have been completed a minimum of two weeks prior to study entry. Treatment with concurrent radiotherapy is not permitted, and prior radiation must have been completed a

minimum of two weeks prior to study entry. Similarly, treatment with radiopharmaceuticals, including alpharadin, must have been completed a minimum of two weeks prior to study entry.

5.3.3 Bone targeted therapy

Concurrent administration of denosumab, or bisphosphonates such as zoledronic acid, is permitted. If a patient is not being treated with any of these agents prior to study entry, he should not begin treatment while on study.

5.3.4. Supportive care medications

Use of growth factor support and antiemetics is permitted at the discretion of the treating physician. Steroids may be given at low-dose maintenance therapy (equivalent of prednisone \leq 10 mg/day) or a short course (\leq 2 weeks) of higher dose therapy.

Low dose oral anticoagulation is allowed provided INR remains < 1.5 from this therapy. Treatment with full dose warfarin is not permitted. Full dose anticoagulation with unfractionated heparin or low molecular weight heparin is permitted.

5.3.5. Other prohibited medications

Subjects should avoid agents known to be Cytochrome P450 (CYP3A4) inducers or inhibitors for the duration of study treatment. See Appendix B for a list of CYP3A4 inducers and inhibitors.

In addition, the following drugs should be avoided throughout the study period because they are known to lower seizure threshold or prolong the QT interval:

- Aminophylline/theophylline
- Atypical antipsychotics (e.g., clozapine, olanzapine, risperidone, ziprasidone)
- Bupropion
- Class IA and III antiarrhythmics (e.g., amiodarone, bretylium, disopyramide, ibutilide, procainamide, quinidine, sotalol)
- Dolasetron
- Droperidol
- Gatafloxacin/moxifloxacin
- Insulin
- Lithium
- Macrolide antibiotics (e.g., erythromycin, clarithromycin)
- Pethidine
- Phenothiazine antipsychotics (e.g., chlorpromazine, mesoridazine, thioridazine)
- Pimozide
- Tricyclic and tetracyclic antidepressants(e.g., amitriptyline, desipramine, doxepin, imipramine, maprotiline, mirtazapine)
- Venlafaxine

5.4 Duration of Therapy

Duration of therapy will depend on individual response, evidence of disease progression and tolerance. In the absence of treatment delays due to adverse events, treatment may continue until one of the following criteria applies:

- Disease progression,
- Intercurrent illness that prevents further administration of treatment,
- Unacceptable adverse event(s),
- Participant demonstrates an inability or unwillingness to comply with the oral medication regimen and/or documentation requirements
- Participant decides to withdraw from the study, or
- General or specific changes in the participant's condition render the participant unacceptable for further treatment in the opinion of the treating investigator.

5.5 Duration of Follow Up

Patients will be followed for survival information every 3 months until death, up to 2 years after discontinuing therapy, or patient is lost to follow-up. If a patient has withdrawn consent, no further follow up will occur.

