1.1 Study Design

We plan to conduct a single arm, open label, combination study with tivozanib and enzalutamide (enz) in men with metastatic castration resistant prostate cancer (mCRPC). All men will receive standard dosing of each drug, with tivozanib administered at 1.5 mg once daily for 3 weeks followed by a one-week break, and enzalutamide taken continuously at 160 mg once daily. Both will be orally administered. A single dose reduction of tivozanib will be permitted, if necessary, to 1.0 mg daily. Patients will continue on treatment until they experience objective or clinical disease progression, or unacceptable toxicity.

Because this combination has not been previously tested, a safety run-in will be conducted at the outset of the trial. While waiting for the first 3 patients to complete one month of treatment, no more than 10 total patients may be enrolled. These patients will be analyzed for safety and toxicity. If any treatment-related, expected or unexpected grade 3 or higher adverse events occur during the first month of treatment in the first 3 patients, or if the rate is >30% among the first 10 patients during the first month of treatment, further accrual will be halted for reconsideration of the appropriateness of the dosing schedules.

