1.3 Secondary Objectives

Secondary objectives will be to demonstrate an acceptable tolerability profile of tivozanib and enz, to estimate overall survival and time to PSA progression, to evaluate PSA and objective response and to explore an angiogenesis signature that may predict benefit from VEGFR-targeted therapy in advanced prostate cancer.

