8. STUDY CALENDAR

Baseline evaluations are to be conducted within 3 weeks prior to start of protocol therapy. Subsequent evaluations should be carried out on Day 1 of subsequent cycles (+/- 3 days) every 12 weeks from Cycle 46 on. Radiographic evaluations including bone and abdominal/pelvic CT scans should be conducted at baseline and every 24 weeks from Cycle 46 on.

| | Pre- Study | Cycle 1 Day 1 ^x | Cycle 2 to Cycle 45, Day 1 ^x | Day 1 Cycles ≥ 46, Every 12 Weeks ^x | Off Study ^b |
|---|---------------|-------------------------------|---|--|------------------------|
| Treatment Schedule: | | | | | |
| Tivozanib | | X (days 1-21) | X (days 1-21) | X (days 1-21) | |
| Enzalutamide | | X (Days 1-28) | X (days 1-28) | X (days 1-28) | |
| Informed consent | X | | | | |
| Demographics | X | | | | |
| Medical/Interval history | X | X | X | X | X |
| Concurrent meds | X | X | X | X | X |
| Physical exam | X | X | X | X | X |
| Vital signs/ BP | X | X | X | X | X |
| Performance status | X | X | X | X | X |
| Serum PSA | X | | X | X | X |
| PT, PT/INR, and PTT | X | | | | |
| CBC w/diff, plts | X | X | X | X | X |
| Serum chemistry ^a | X | X | X | X | X |
| Serum testosterone | X | | | | |
| Thyroid Function (TSH only) | X | | X (odd cycles) | X | |
| Urinalysis (urine protein only) | X | X | X | X | X |
| Chest xray | X | | as clinicall | y indicated | |
| Bone scan and abdominal/pelvis CT scans | X | Rep | Repeat scans every 24 weeks | | X ^c |
| EKG | X | | | | |
| Adverse Event Evaluation | X | Х | | | -X |
| Survival follow-up | | | | | X ^d |

x: ± 3 days for treatment or assessment requirement

MEASUREMENT OF EFFECT

a: Sodium, potassium, chloride, BUN, creatinine, glucose, albumin, total protein, total bilirubin, alkaline phosphatase, SGOT [AST], SGPT [ALT]

b: Off-study evaluation should occur within 30 days after the last dose of study treatment c: Post-treatment scans will be performed if an assessment has not been performed within the prior 6 weeks

d: Follow for survival information every 3 months until death, up to 2 years after discontinuing therapy, or patient lost to follow-up

The primary endpoint of the study is progression free survival (PFS). Secondary clinical endpoints will include safety, overall survival, time to PSA progression, PSA response rate and objective response rate.

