9.2.2 Overall survival

The duration of overall survival will be calculated for all patients from the date of registration until the date of death due to any cause.

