14.3. Analysis of Secondary Endpoints

Secondary clinical endpoints will include toxicity, overall survival, time to PSA progression, objective response rate and PSA response rate.

We will monitor toxicities experienced by all treated patients on the study. With 42 patients, the maximum width of a 90% CI for a given toxicity rate is 27%. The probability of observing at least one rare severe toxicity (true rate=5%) is 88%.

Objective and PSA response will be estimated as the number of responders divided by the total number of evaluable patients. Exact binomial confidence intervals will be calculated for the true response proportion.

Distribution of overall survival defined as the time from registration to death due to any cause will be estimated using Kaplan-Meier methods. PSA progression will be defined according to the recommendations of PCWG2¹⁵.

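### Stopping survival follow-up 2 years after each man leaves therapy makes Kaplan-Meier OS censoring depend on time on therapy after month 24; the bias is modest and probably, not certainly, upward

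*Combined protocol and SAP*

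**What the plan says.** Estimating OS is a secondary objective: Section 1.3 sets out "to estimate overall survival and time to PSA progression". Section 9.2.2 counts OS "from the date of registration until the date of death due to any cause", and Section 14.3 gives the method: "Distribution of overall survival defined as the time from registration to death due to any cause will be estimated using Kaplan-Meier methods".

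Survival contact is limited relative to each man's own stop date. Section 5.5 has men "followed for survival information every 3 months until death, up to 2 years after discontinuing therapy", and footnote d of the Section 8 calendar repeats it: "Follow for survival information every 3 months until death, up to 2 years after discontinuing therapy, or patient lost to follow-up". Section 5.5 also states: "If a patient has withdrawn consent, no further follow up will occur".

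The stop date is not arbitrary. Section 1.1 says: "Patients will continue on treatment until they experience objective or clinical disease progression, or unacceptable toxicity". Section 5.4 adds intercurrent illness, worsening of the participant's condition, non-compliance and withdrawal.

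The documents give no OS censoring rule, OS analysis date, common survival cut-off or sensitivity analysis for dependent censoring.

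**The concern.** OS is measured from registration, but observation ends at a time measured from treatment stop. A living man who stops at month 3 leaves the OS risk set at month 27; one who stops at month 22 stays until month 46. After month 24 the cap therefore removes surviving early stoppers and keeps men who stayed on therapy longer. Kaplan-Meier treats the removed men as having the same future as those who remain, which is doubtful when most stops mark progression or deterioration.

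What is at stake is how the later part of a descriptive OS curve, and possibly median OS, is read. Two features make it worth settling. The calendar makes provision for Cycle 46 onward (day 1 is 45 × 28 = 1,260 days, about 41 months), so survival data well past month 24 are foreseen. The study has one arm, so no control group shares the distortion.

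**Working it through.** **Inputs from the documents.** The cap is 24 months after stopping (5.5, footnote d). Median PFS, used as a proxy for time on therapy, is 14 months (null) or 22.4 months (target) in Section 14.1, and 8.3 months after chemotherapy in Section 2.3. Section 14.2 plans 42 men, 21 months of accrual and 6 more of follow-up.

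**Assumptions.** Survival after stopping is not in the documents. I take a median of 10 to 24 months, first exponential and independent of time on therapy, then with a falling hazard. Deaths on therapy are ignored.

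**The plan's own figures.** The plan states no OS figure. Its PFS hazards reproduce: ln 2/14 = 0.0495 and ln 2/22.4 = 0.0309.

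**Onset.** Censoring time = time on therapy + 24, which is at least 24 months. The rule censors nobody before month 24, so its bias to that point is zero whatever the model.

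**Worked case: 14 months on therapy, 18 months after stopping.** Let a = ln 2/14 = 0.0495 and b = ln 2/18 = 0.0385, so a/(a-b) = 4.5 and b/(a-b) = 3.5.

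True OS(t) = [a·exp(-bt) - b·exp(-at)]/(a-b). At 48 months this is 4.5 × 0.1575 - 3.5 × 0.0929 = 38.4%. Those survivors divide as follows:
- on therapy: exp(-48a) = 9.3%
- stopped within the last 24 months: 4.5 × [exp(-24a-24b) - exp(-48a)] = 4.5 × (0.1209 - 0.0929) = 12.6%
- stopped more than 24 months ago, no longer followed: 4.5 × [exp(-48b) - exp(-24a-24b)] = 4.5 × (0.1575 - 0.1209) = 16.5%

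The true monthly hazard at month 48 is 0.0385 × (12.6 + 16.5)/38.4 = 0.029. Among men still followed it is 0.0385 × 12.6/(9.3 + 12.6) = 0.022. Kaplan-Meier accumulates the lower figure. Its large-sample value is exp(-∫ observed hazard), which numerical integration and simulation both put at 42.2% at 48 months.

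| Month | True OS | Kaplan-Meier under the cap | Difference (points) |
|---|---|---|---|
| 24 | 71.9% | 71.9% | 0 |
| 36 | 53.6% | 55.1% | +1.5 |
| 48 | 38.4% | 42.2% | +3.9 (unrounded) |

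Median OS reads about 40.4 months against a true 38.6.

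**Range, exponential and independent, post-stop median 10 to 24 months.**
- Time on therapy 14 or 22.4 months: about +1 to +1.5 points at 36 months and +3 to +4 at 48.
- Time on therapy 8.3 months: about +2 points at 48 months (1.9 to 2.5).
- Adding positive correlation between the two periods (Gaussian copula 0.5) to the 14- and 22.4-month cases widens the 48-month range to +1.7 to +6.1.

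**Falling post-stop hazard.** Use post-stop survival (1 + vθu)^(-1/v), a gamma frailty with variance v, and θ = (2^v - 1)/(v × median). With an 18-month median, the 48-month differences are:

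| Median time on therapy | v = 1 | v = 2 |
|---|---|---|
| 8.3 | about -2 | about -4 |
| 14 | +0.1 | -1.6 |
| 22.4 | about +1 | 0 |

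Across post-stop medians of 10 to 24 months the range is about +2 to -4. The sign can turn because the men dropped have already survived 24 months after stopping; if the hazard falls, they are a low-risk group. If stop time is unrelated to death, the bias is zero.

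**Against sampling error.** Simulating 42 men in the 14/18 case gives a standard deviation of 8.1 points at 36 months and 8.8 at 48.

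**Against calendar time.** At month 27 (21 + 6), only 42 × 3/21 = 6 men could have more than 24 months of follow-up, and the cap is expected to censor about 0.2 men. In the 14/18 case that rises to about 2 by month 36, 8 by month 48 and 12 by month 60. The long-run share is 2^(-24/18) = 40%.

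**The case against.** A reader might infer that the rule always inflates OS. The documents do not support that. They give no survival after stopping, and a falling post-stop hazard, as plausible a priori as a constant one, makes the error nil or negative. Men also stop for toxicity, non-compliance or a hold of 4 weeks or more (5.1.2), so the men dropped are not all early progressors. This part of the objection stands.

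A reader might also infer that a distorted OS curve would mislead the decision on further study. Section 14.1 ties that decision to a median PFS of 22.4 months. OS has no test, comparator, threshold or landmark. The background on earlier antiangiogenic trials, which gained PFS without gaining OS, explains interest in OS but sets no rule. This also stands.

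The effect is small beside sampling error, and almost absent if OS is reported near month 27. The only enzalutamide median OS in the documents, 18.4 months in previously treated men (2.1.2, 2.3), falls before month 24, where the rule does no harm. That figure does not settle the chemotherapy-naive case.

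What the objection does not remove is the dependence itself. Sampling error shows in a confidence interval; dependent censoring does not, and it moves the interval as well.

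**Conclusion.** The point holds in limited form. After month 24 the cap ties OS censoring to time on therapy, which the plan ties largely to prognosis, and nothing in the plan corrects for it. The error is probably upward if stopping marks a lasting rise in the death hazard, but neither sign nor size can be fixed from the documents. The 36- and 48-month figures above rest on PFS as a proxy for time on therapy and on an assumed post-stop survival. The 24-month result needs neither assumption. This is a minor weakness in a secondary, untested estimate, and the primary PFS design is untouched.

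**What to change.** In Section 5.5 and calendar footnote d, replace the per-man cap with one rule: every consenting man is followed for survival until death or a single study-wide cut-off date. Censoring then no longer depends on when he stopped, and the bias from this rule disappears.

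If the 2-year cap is kept, add a sentence to Section 14.3 stating either that Kaplan-Meier OS is reported only to 24 months from registration, or that later estimates are subject to censoring that depends on the stop date.

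The first option costs longer 3-monthly vital-status contacts for some of at most 42 men. Limiting the curve to 24 months needs no extra follow-up, but median OS may then not be reportable. The caveat costs nothing, but leaves the bias in place.
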